4.1.5 Blinding and procedures for unblinding

4.1.5.1 Blinding

Patients, investigators, central reviewers, and everyone involved in trial conduct or analysis or with any other interest in this extension will remain blinded to the medication provided at Visit 1 at least until the last patient from the 1368-0052 trial completes █ weeks of treatment in this trial. The access to the randomisation code for Visit 1 will be kept restricted until its release for analysis.

4.1.5.2 Unblinding and breaking the code

Emergency unblinding will be available for the blinded medication at Visit 1 only. Although, all patients will receive spesolimab regardless at all visits. All patients at Visit 1 will be receiving placebo plus spesolimab.

4.1.6 Packaging, labelling, and re-supply

The IMP will be provided by BI or a designated contract research organization (CRO). They will be packaged and labelled in accordance with the principles of Good Manufacturing Practice. Re-supply to the sites will be managed via an IRT system, which will also monitor expiry dates of supplies available at the sites. For details of packaging and the description of the label, refer to the ISF.

4.1.7 Storage conditions

Drug supplies will be kept in their original packaging and in a secure limited access storage area according to the recommended storage conditions on the medication label. A temperature log must be maintained for documentation. If the storage conditions are found to be outside the specified range, the Clinical Research Associate (CRA) (as provided in the list of contacts) must be contacted immediately. Trial medication must be securely stored, e.g. in a locked refrigerator at the site or at a pharmacy. The medication may only be dispensed to trial patients according to the CTP by authorized personnel as documented in the trial staff list.

4.1.8 Drug accountability

The investigator or designee will receive the investigational drugs delivered by the sponsor when the following requirements are fulfilled:

- Approval of the CTP by the institutional review board (IRB) / independent ethics committee (IEC)
- Availability of a signed and dated clinical trial contract between the sponsor or delegate and the investigational site,
- Approval/notification of the regulatory authority (RA), e.g. competent authority (CA),
- Availability of the curriculum vitae of the Principal Investigator,
- Availability of a signed and dated CTP,
- Availability of the proof of a medical license for the Principal Investigator, if applicable,
- Availability of U.S. Food & Drug Administration (FDA) Form 1572 (if applicable).

Investigational drugs are not allowed to be used outside the context of this protocol. They must not be forwarded to other investigators or clinics.

The investigator or designee must maintain records of the product's delivery to the trial site, the inventory at the site, the use by each patient, and the return to the sponsor or warehouse / drug distribution centre or alternative disposal of unused products. If applicable, the sponsor or warehouse / drug distribution centre will maintain records of the disposal.

These records will include dates, quantities, batch / serial numbers, expiry ('use- by') dates, and the unique code numbers assigned to the IMP and trial patients. The investigator or designee will maintain records that document adequately that the patients were provided the doses specified by the CTP and reconcile all IMP received from the sponsor. At the time of return to the sponsor and/or appointed CRO, the investigator or designee must verify that all unused or partially used drug supplies have been returned and that no remaining supplies are in the investigator's possession.

4.2 OTHER TREATMENTS, EMERGENCY PROCEDURES, RESTRICTIONS

4.2.1 Other treatments and emergency procedures

Systemic steroids dosed i.v. or orally for less than 24 hours as treatment of infusion or anaphylactic reactions are permitted and do not lead to treatment discontinuation nor to assignment as treatment failures in the ITT analysis.

Any of the below treatments in this section must be documented in the source data, including an estimate on dispensed medication, and documented in CRF (concomitant medications) and the corresponding AE if applicable.

4.2.1.1 Systemic hypersensitivity including infusion reaction and anaphylactic reaction

In case of systemic hypersensitivity including infusion reaction and anaphylactic reaction emerging during or after infusion / injection(s) of trial medication, the investigator should consider in accordance with severity of the reaction and local SoC to:

- Immediately interrupt the infusion (if i.v.) or stop further injections (if s.c.).
- Treat with systemic anti-histamines, i.v. steroids, and in case of a severe allergic reaction (e.g., anaphylactic reaction) epinephrine.
- In case of s.c. administration give epinephrine in case of signs of hypersensitivity and add further treatments, e.g. oxygen, i.v. fluids, antihistamines and systemic corticosteroids as needed.

Also draw a plasma sample for IgE and ADA as detailed in the Lab Manual in the ISF (Central laboratory). Consider also the evaluation of histamine, serum tryptase, and complement components.

In case of infusion reaction, based on patient's clinical course and medical judgment, the infusion may be re-initiated in case of mild or moderate infusion reactions (according to Rheumatology Common Toxicity Criteria (RCTC) grading) at lower speed with gradual increase to complete the infusion as detailed in the Instructions for Pharmacist in the ISF. In any case, the total duration of infusion should not exceed 180 minutes (3 hours). If the infusion exceeds 180 minutes, it should be stopped and the infusion should be skipped. Patient should be called for the next scheduled visit as planned.

In case of systemic hypersensitivity, based on patient's clinical course and medical judgment, the injection(s) may be continued in case of mild or moderate systemic hypersensitivity

(according to RCTC grading) to complete the injections as detailed in the Instructions for Use of Spesolimab Pre-filled Syringes in the ISF.

In case of anaphylactic reaction based on the criteria discussed in the statement paper from Sampson HA ([Appendix 10.1 \[R11-4890\]](#)) suspected to be caused by the trial medication, the investigator should discontinue treatment permanently with spesolimab.

When a non-acute hypersensitivity reaction related to immune complexes (i.e., serum sickness) is suspected, please draw a sample for the laboratory assessment for circulating immune complexes.

In case of severe infections (according to RCTC grading), serious infections, opportunistic or mycobacterium tuberculosis (TB) infections, treatment of the infection should be initiated promptly according to local SoC. No further trial medication should be administered until the active infection has resolved. Treatment with spesolimab may be restarted when the patient has recovered according to investigator's assessment.

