
Infections
	
Inhibition of the immune response with an immunomodulating biologic may increase the risk of infections.
 
A recent characterization of individuals with homozygous IL36R KO mutations revealed that normal immune function was broadly preserved suggesting that IL36 signaling pathway inhibition does not compromise host defenses [R17-3632].
	
Infection testing procedures will be established for this trial. Treatment of infections should be initiated promptly according to standards of care.
 
Patients with infections such as human immunodeficiency virus (HIV), viral hepatitis or tuberculosis are discontinued from the trial. However, if latent tuberculosis is established during the trial, then patients can receive anti-tuberculosis treatment as per investigator discretion and continue receiving study medication as per investigator. Refer to Sections 3.3.4.1 and 6.2.1.2
 
Severe infections and opportunistic infections are considered AESIs for this trial. These conditions and serious infections are subject to close monitoring. Refer to Section 5.2.6.1.4.

Malignancies
	
Inhibition of the immune response with an immunomodulating biologic may increase the risk of a decreased immune defense against malignancies.
 
A recent characterization of individuals with homozygous IL36R KO mutations revealed that normal immune function
	
Patients with a recent history of malignancy will be excluded from participation in this trial. In case of occurrence of malignant neoplasm other than appropriately treated basal cell carcinoma or squamous cell carcinoma of the skin or in situ carcinoma of uterine cervix, the

Possible or known risks of clinical relevance for this trial	Summary of data, rationale for the risk	Mitigation strategy
	
was broadly preserved suggesting that IL36 signalling pathway inhibition does not compromise host defenses. [R17-3632].
	
investigator should discontinue treatment with spesolimab. Diagnostics and treatment have to be initiated according to local SoC. Malignancies represent always SAEs and are subject to close monitoring. Refer to Section 5.2.6.1.3.

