3.3.4.1 Discontinuation of trial treatment

An individual patient will discontinue trial treatment if:

- The patient wants to discontinue trial treatment, without the need to justify the decision.
- The patient has repeatedly shown to be non-compliant with important trial procedures and, in the opinion of both, the investigator and sponsor representative, is not willing or able to adhere to the trial requirements in the future.

- The patient develops infections such as HIV, viral hepatitis or tuberculosis. However, if latent tuberculosis is diagnosed during the trial, patients can receive anti-tuberculosis treatment as per investigator discretion and continue receiving study medication as per investigator. Refer to [Section 6.2.1.2](#)
- The patient needs to take concomitant medication such as immunosuppressive biologics, live vaccines, or other concomitant medication that interferes with the Investigational Medicinal Products (IMP) or other trial treatment. Also refer to [Sections 4.2.1](#) and [4.2.2](#).
- The patient can no longer receive trial treatment for medical reasons such as surgery, serious or severe Drug Induced Liver Injury attributable to the trial drug, other adverse events, other diseases, or pregnancy. Also refer to [Sections 5.2.6.1.4](#) and [5.2.6.2.3](#).
- The patient develops suicidal ideation of type 4 or 5 in the C-SSRS (i.e. active suicidal thoughts with method and intent but without specific plan, or active suicidal thoughts with method, intent and plan) or any suicidal behaviour (i.e. actual attempt, interrupted attempt, aborted attempt, or preparatory acts or behaviour). The patient should immediately be referred to a mental health professional for further work-up.
- The patient is a Non-responder on 1200 mg of IMP and there is no change or no improvement in their HS-PGA grade at Week 24 compared to Week 12.

In addition, the principal investigator may discontinue subjects at any time based on his or her clinical judgment.

For individual stopping rules related to specific AEs, please see [Section 4.2.1](#).

In case of a temporary reason, trial treatment should be restarted if medically justified, please see [Section 4.1.4](#).

For all patients the reason for withdrawal from trial treatment (e.g. adverse events) must be recorded in the CRF. This data will be included in the trial database and reported.

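### The protocol does not settle whether a patient who develops active tuberculosis may return to spesolimab, or who must agree

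*Protocol*

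**What the plan says.** **Discontinuation texts.** Protocol 3.3.4.1, in its list of reasons for an individual patient to discontinue trial treatment, includes: "The patient develops infections such as HIV, viral hepatitis or tuberculosis". The one tuberculosis exception follows at once: "However, if latent tuberculosis is diagnosed during the trial, patients can receive anti-tuberculosis treatment as per investigator discretion and continue receiving study medication". The infections row of Table 1.4.2:1 (Section 1.4.2) says that patients with infections such as HIV, "viral hepatitis or tuberculosis are discontinued from the trial", with the same exception for latent disease.

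**Interruption text.** The infections paragraph at the end of 4.2.1.1 covers severe and serious infections and also names "opportunistic or mycobacterium tuberculosis (TB) infections, treatment of the infection should be initiated promptly according to local SoC". It continues: "No further trial medication should be administered until the active infection has resolved". It then says: "Treatment with spesolimab may be restarted when the patient has recovered", with recovery judged by the investigator.

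**Linking texts.** After its list, 3.3.4.1 says "For individual stopping rules related to specific AEs, please see" and names Section 4.2.1. It also allows restart after a temporary reason and sends the reader to 4.1.4, where restart is decided individually once the sponsor has been consulted. The section closes by saying that patients who stop treatment stay in the trial for the early-discontinuation and follow-up procedures, if they agree.

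**The concern.** Two sites could each follow the protocol and handle the same patient differently. One, reading 3.3.4.1 or the risk table, would end treatment. The other, reading 4.2.1.1, would hold treatment, wait for recovery and restart on its own judgement.

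Tuberculosis is an adverse event of special interest (Protocol 5.2.6.1.4; SAP 7.8.1), so re-exposure after it should not depend on which page a site opens. The rules also have to work after exposure has begun. Section 3.3.3 has no exclusion criterion that names tuberculosis. According to 6.2.1.2, the Visit 1 infection results arrive only after the first dose, and negative tests are repeated every 52 weeks.

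**Working it through.** No arithmetic applies; the check sets the texts side by side for a patient with active tuberculosis.

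| Question | 3.3.4.1 | Table 1.4.2:1 | 4.2.1.1 | 4.1.4 |
|---|---|---|---|---|
| Dosing during active disease? | Stopped | Stopped | Stopped until resolved | Not addressed |
| Return to treatment after recovery? | Not stated for tuberculosis; restart only for a temporary reason | Does not fit with leaving the trial | Allowed | Allowed after a temporary reason |
| Who must agree? | Refers to 4.1.4 | Not stated | Investigator | Sponsor consulted, case by case |
| Patient stays in the trial? | Yes, for follow-up | No, if read literally | Implied by restart | Implied by restart |

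1. *First row.* The texts that address it agree: nobody is told to dose through active tuberculosis.

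2. *Second row.* Section 4.2.1.1 permits a return. Section 3.3.4.1 permits one only if active tuberculosis counts as a temporary reason, and no text says that it does. The latent-disease exception does not help, because it concerns uninterrupted dosing in a different condition. The table's wording leaves no room for a return.

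3. *Third row.* Suppose that active tuberculosis is a temporary reason. Then 3.3.4.1 leads to 4.1.4 and to sponsor consultation, while 4.2.1.1 asks only for the investigator's judgement. A site that relies on 4.2.1.1 alone could restart without the consultation that 4.1.4 requires. The disagreement therefore survives the most favourable reading.

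4. *Fourth row.* The table and the closing text of 3.3.4.1 disagree on whether stopping treatment also ends participation.

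5. *Navigation.* The infection bullet in 3.3.4.1 refers to 6.2.1.2. The table refers to 3.3.4.1 and 6.2.1.2 for this rule. Section 6.2.1.2 gives a rule for latent disease only and sends the reader back to 3.3.4.1. None of these entries points to the infections paragraph, which has no heading of its own and sits under a hypersensitivity title. The only route to it is the general reference to 4.2.1, which sets no precedence.

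6. *Viral hepatitis, by inference only.* Section 5.2.6.1.4 lists HBV reactivation among the opportunistic infections. Opportunistic infections fall under the restart permission in 4.2.1.1, while viral hepatitis is a discontinuation reason in 3.3.4.1. Section 4.2.1.1 does not name hepatitis, so this is secondary.

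7. *Effect on the analysis.* SAP 6.6.1 reports withdrawal reasons as recorded on the eCRF. SAP 6.3 handles treatment discontinuation by treatment policy. SAP 6.1 ends the on-treatment period 112 days after the actual last dose. These definitions work whichever rule a site follows. One affected patient would have a different last dose, and so a different exposure, disposition and time at risk; one patient in 45 is 1/45 = 2.2%.

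**The case against.** The best defence reads the passages in sequence: 3.3.4.1 is the general list, and 4.2.1 gives the event-specific detail to which it refers. The protocol does use discontinuation for reversible stops: 4.2.1.4 discontinues temporarily for suspected neuropathy, and 4.1.4 speaks of temporary reasons. Where it means a permanent stop it can say so, as 4.2.1.1 does for anaphylaxis. On this view a patient with tuberculosis discontinues, recovers and may restart. The risk table is then only a loosely worded summary that itself defers to 3.3.4.1.

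Much of this stands. A reader might infer that sites hold two opposite stopping rules, a permanent stop against continued exposure. The documents do not support that: every text that addresses dosing in active disease stops it, and none calls the tuberculosis stop permanent. Nor can the hepatitis point be called an express contradiction, or the summary tables be said to be materially distorted.

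The defence still does not close the gap. It needs active tuberculosis to be a temporary reason, which no text says. It leaves the conflict over sponsor consultation untouched. And it has to set aside the plain wording of the risk table.

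**Conclusion.** The protocol is wrong as written on a narrow point: whether a patient who has recovered from active tuberculosis may resume spesolimab, and on whose agreement. The risk table adds a second, smaller inconsistency on whether such a patient stays in the trial. The same tension for viral hepatitis is an inference.

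The size cannot be computed, because the documents give no event rate. Few cases are likely in about 45 patients, and the trial is descriptive with no hypothesis test, so the effect on the summary tables is minor. What matters is the handling of the individual patient after an event of special interest. The conclusion rests on the current protocol text and on reading the table's wording literally. It takes no view on which clinical rule is right.

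**What to change.** Reconcile Table 1.4.2:1, 3.3.4.1 (the infection bullet, the restart clause and the closing text on staying in the trial), 4.1.4 and the infections paragraph of 4.2.1.1. The result should be one rule that states:

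- whether restart after active tuberculosis is possible at all;
- if it is, whether the investigator alone decides or the sponsor must be consulted;
- whether a patient who stops treatment stays in the trial for follow-up;
- whether the same rule covers viral hepatitis, including HBV reactivation.

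Cross-refer the infection bullet and the risk table to the infections paragraph, and give that paragraph its own heading. The sponsor must decide which rule applies.

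The cost is a wording clarification in the protocol. The design, the sample size and the SAP definitions need no change.

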4.2.1.2 Malignancies

In case of occurrence of malignant neoplasm other than appropriately treated basal cell carcinoma or squamous cell carcinoma of the skin or in situ carcinoma of uterine cervix, the investigator should discontinue treatment with spesolimab. Diagnostics and treatment have to be initiated according to local SoC.

4.2.1.3 Suicidality

In case of signals of suicidal ideation or suicidal behaviour the patient should be referred to psychiatric work up. Overall, the choice of SoC treatment will be left at the discretion of the investigator. The sponsor will not provide/supply SoC treatment (s) to the sites. See [Section 5.2.5.2](#).

4.2.1.4 Peripheral Neuropathy

If peripheral neuropathy is suspected, treatment with spesolimab should be temporarily discontinued until a full neurological investigation has been conducted.

After completion of the neurological investigation, treatment can be restarted based on medical judgement of the investigator.

4.2.2 Restrictions

4.2.2.1 Restrictions Regarding Concomitant Treatment

The medication (or classes of medications) listed in [Table 4.2.2.1:1](#) are restricted for specific periods during the study (W0 - W12 and W12 through to EoT). As these restricted medications are consistent with the preceding 1368-0052 PoCC trial, patients must not have taken the medications (or classes of medications) through to the EoT Visit of the PoCC trial (which is the same day as Visit 1 in this trial). In the event that the EoT/V1 cannot be done on

the same day then a maximum 2-week gap can be allowed from the EoT Visit of the 1368-0052 PoCC trial to Visit 1 of this extension trial, systemic and topical antibiotics can be used for disease worsening as per investigator discretion. However, biologics, immunomodulators and opioid analgesics are not allowed for HS and non-HS indications. See also footnote to Visit 1 in the [Flow Chart](#).

Table 4.2.2.1: 1 – Restricted Medications

Medication	W0 - W12	W12* - EoT
Systemic antibiotics ¹	Restricted for HS	Permitted for HS-disease worsening
Systemic corticosteroids ²	Restricted for HS	Restricted for HS
Biologics causing immunosuppression	Restricted for HS and non-HS indications	Restricted for HS and non-HS indications
Other systemic immunomodulatory agents	Restricted for HS and non-HS indications	Restricted for HS and non-HS indications
Live vaccines ³	Restricted	Restricted
Opioid analgesics	Restricted for HS	Restricted for HS
Spirolactone ⁴	Restricted for HS and non-HS indications	Restricted for HS
Metformin ⁴	Restricted for HS and non-HS indications	Restricted for HS
Topical cannabis oil ⁵	Restricted for HS	Permitted
Systemic medicinal cannabis	Restricted for HS and non-HS indications	Restricted for HS
Topical corticosteroids for HS	Restricted for HS ⁶	Permitted

*Following Week [redacted] dose modification management – See [Table 3.1: 1](#)

1. For more information on the use of systemic antibiotics please see [Section 4.2.2.3](#).
2. Systemic corticosteroids as short courses, i.e., approximately 1- 2 weeks at the discretion of the investigator, can be used for indications other than HS.
3. Patients can receive seasonal influenza vaccines (excluding live attenuated vaccines).
4. Restricted if used for HS. Allowed for non-HS indications as a stable dose prior to V2 of the 1368-0052 PoCC trial.
5. Restricted if used over HS-affected areas. Other alternative therapies for HS are restricted, unless permitted after discussion with the PI and the sponsor.
6. Prior to Week [redacted], topical corticosteroids are allowed for indications other than HS, if the areas are not affected by HS concurrently.

4.2.2.2 Rescue Treatment

HS Disease worsening is defined as a 150% increase in AN count from baseline. Rescue medication is defined as the treatment for disease worsening, and includes systemic antibiotics or immunosuppressive biologics such as TNF-inhibitors. The sponsor will not provide/supply these treatment(s) to the sites. As per [Table 4.2.2.1: 1](#), immunosuppressive biologics are restricted during the entire trial. If a patient receives rescue treatment, the decision to maintain the patient on trial treatment is based on the investigator's clinical judgement.

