4.2.2.3 Antibiotic Use During the Trial

Non HS use:

Systemic antibiotics can be used for indications other than HS. A maximum of 4 weeks of systemic antibiotics are allowed from Week 0 - Week 12 for non-HS indications.

HS disease worsening (as defined above in [Section 4.2.2.2](#)):

After Week 12, systemic antibiotics may be used for disease worsening as per investigator discretion.

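### Protocol 4.2.2.2 leaves staying on spesolimab after any rescue, immunosuppressive biologics included, to the investigator, while Protocol 3.3.4.1 requires spesolimab to stop

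*Protocol*

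**What the plan says.** **Rescue (Protocol 4.2.2.2).** The definition covers two classes: "Rescue medication is defined as the treatment for disease worsening, and includes systemic antibiotics or immunosuppressive biologics such as TNF-inhibitors". The section then notes that "immunosuppressive biologics are restricted during the entire trial". It ends: "If a patient receives rescue treatment, the decision to maintain the patient on trial treatment is based on the" investigator's judgement. That sentence refers to rescue treatment in general and has no exception for biologics.

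**Stopping (Protocol 3.3.4.1).** The list opens with "An individual patient will discontinue trial treatment if", and one of its items is "The patient needs to take concomitant medication such as immunosuppressive biologics, live vaccines". There is no exception for rescue. The same item sends the reader to Sections 4.2.1 and 4.2.2.

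**Restrictions (Protocol 4.2.2.1 and 4.2.2.3).** The row "Biologics causing immunosuppression" in Table 4.2.2.1: 1 restricts these drugs for HS and non-HS use up to the end-of-treatment visit. For antibiotics the position differs: "After Week 12, systemic antibiotics may be used for disease worsening as per investigator discretion". Protocol 7.2.1 makes concomitant use of restricted medication an important deviation.

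**Adverse event window (Protocol 2.1.2 and 7.2.5).** The primary endpoint is the occurrence of treatment-emergent adverse events from first dose to 16 weeks after the last dose.

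**Censoring of efficacy data (SAP).** Section 6.3 lists three intercurrent events: rescue while on treatment, and treatment discontinuation with or without restricted medication. Its hybrid strategy (EC-H) treats only rescue hypothetically and uses treatment policy for the others. Section 7.5.2 adopts that strategy for continuous secondary endpoints, then censors after an intercurrent event that it does not name. Section 7.6.1 refers to the censoring described for the primary endpoint, which has none.

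**The concern.** For one event, a TNF-inhibitor given for worsening HS, a site finds two instructions. One says that spesolimab stops; the other says that the investigator decides. The protocol gives no order of precedence. The cross-reference in the stopping rule does not help, because it leads back to the part of the protocol that holds the discretionary sentence. Protocol 1.4.1 also offers rescue to patients who worsen and does not name receipt of rescue as a reason to discontinue.

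Two things are at stake. The first is safety: Protocol Table 1.4.2:1 names infection as a possible risk of an immunomodulating biologic, and severe and opportunistic infections are adverse events of special interest. The second is attribution: in a single-arm trial whose primary endpoint is treatment-emergent adverse events, events on two such drugs would be tabulated as events on spesolimab.

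**Working it through.** The plan states no figure for this point, so there is none to reproduce. The main check sets the texts side by side; the arithmetic only illustrates the consequence.

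**1. The texts, for a patient given a TNF-inhibitor for HS worsening**

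| Source | Instruction on spesolimab |
|---|---|
| Protocol 3.3.4.1 | Stop (mandatory) |
| Protocol 4.2.2.2, last sentence | Investigator decides |
| Protocol Table 4.2.2.1: 1 | Biologic restricted; silent on spesolimab once it has been given |
| Protocol 7.2.1 | Important deviation; silent on spesolimab |

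The first two rows differ, and the last two do not settle the difference.

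**2. Biologic use inside the adverse event window**

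Inputs:
- Residual effect period: 16 weeks (Protocol 1.2.3).
- Last dose: the week is blacked out, so it is inferred. Visits 8 to 52 are two-weekly from Week 14 (Flow Chart), so Visit 52 is at Week 14 + 2 × (52 − 8) = 102. The end-of-treatment visit is Visit 53 (SAP Table 6.7: 1), hence about Week 104. Study drug is given at that visit (Flow Chart), and Protocol 6.2.3 dates the last dose to it. Week 98 is only the last lesion count listed in Flow Chart footnote 17.
- Start of the biologic: Week 26, assumed. Its use is assumed uninterrupted to the end of the window.

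Results:
- Spesolimab stops at Week 26: the window closes at 26 + 16 = Week 42, so 42 − 26 = 16 weeks of biologic use fall inside it. If the last spesolimab dose came before the biologic started, the figure is smaller.
- Spesolimab continues: the window closes at 104 + 16 = Week 120, so 120 − 26 = 94 weeks fall inside it.
- Range if spesolimab continues: 120 − 14 = 106 weeks for a start at Week 14, and 120 − 86 = 34 weeks for a start at Week 86.

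**3. The censoring wording in the SAP**

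| Source | Data excluded |
|---|---|
| SAP 6.3 (EC-H) | Only rescue is handled hypothetically |
| SAP Table 6.4: 1, definition of OC | After rescue |
| SAP 6.6.2, OC rule | After rescue |
| Protocol 7.2.3 | After rescue |
| SAP 7.5.2 | After an unnamed intercurrent event, under EC-H and with OC |

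The first four sources agree, and SAP 7.5.2 invokes both EC-H and OC. A programmer who follows those references censors after rescue only. Table 6.4: 1 assigns OC or OC-NRI to the further endpoints too, so the faulty pointer in 7.6.1 does not change what is done there.

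**The case against.** The best defence is that the protocol is coherent when read as a whole. No section authorises a biologic alongside spesolimab. The restriction stands immediately before the discretionary sentence, the table repeats it through to end of treatment, and the stopping rule is mandatory and specific to the drug class. A specific, mandatory rule would ordinarily govern over a general discretion. Antibiotics after Week 12 are the named rescue that is permitted, and they give the discretion a sensible scope. Any dual exposure would also be visible: restricted medication is an important deviation, such deviations are listed per patient (SAP 7), and rescue is tabulated by preferred name (SAP 7.6.2).

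Much of this stands. It makes the antibiotics-only reading the likely intention and limits the harm. It does not remove the defect: the sentence covers all rescue, in a section that has just named biologics as rescue. Visibility in the report comes after the patient has received both drugs.

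Two stronger readings are tempting, and the documents support neither:
- A reader might infer that the protocol permits a biologic with spesolimab. It does not; it restricts biologics throughout and only fails to exclude them from the discretion.
- A reader might infer from SAP 7.5.2 that data after treatment discontinuation are discarded, and that this removes poor values from patients stopped under the rule for "no change or no improvement in their HS-PGA grade at Week 24 compared to Week 12". The sources in the working show a rescue-only rule. In addition, the Flow Chart recommends that reassessment at the start of the visit and allows that visit to serve as the end-of-treatment visit, so the poor value can be recorded at the decision to stop and not after it.

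**Conclusion.** The conflict between Protocol 4.2.2.2 and 3.3.4.1 is real and should be corrected, because it bears on patient safety and on attribution of the primary endpoint. Its size in practice is unknown: it depends on how many patients receive a biologic for HS worsening while on spesolimab, which may be none. The contrast of 16 and about 94 weeks is illustrative. It rests on an assumed start at Week 26, uninterrupted use of the biologic, and a last dose inferred to be near Week 104.

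The SAP wording is a minor clean-up with no expected effect on results. SAP 5.4.3, which is cited for the definition of rescue therapy, is not visible in the public text; its absence is not counted against the plan, and nothing here depends on it.

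**What to change.** **Protocol 4.2.2.2.** Replace the last sentence with: *After rescue with anything other than an immunosuppressive biologic, the investigator decides whether spesolimab continues. A patient who needs an immunosuppressive biologic must discontinue spesolimab (Section 3.3.4.1).* The definition of rescue is not an exhaustive list, so framing the discretion as everything except these biologics leaves no other rescue treatment without a rule.

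**SAP 7.5.2.** Name use of rescue therapy, in both places, as the event after which data are censored.

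**SAP 7.6.1.** Refer to Section 7.5.2 in place of the primary endpoint.

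SAP 6.3 stays as it is. The cost is one protocol passage and two SAP phrases. No data are lost, the estimand does not change, and continuing spesolimab after antibiotic rescue remains allowed.
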